2.5.3 Exploratory Outcome Measures

1. Changes in serum concentrations of TMAO, carnitine, and phosphatidylcholine within participants and between High-S vs. Low-S diets.

3 RESEARCH DESIGN AND METHODS

This is a randomized, 4- to 5-week crossover pilot study of 15 highly motivated healthy volunteers who will consume two 7-day intervention diets: 1) a diet low in sulfur-containing amino acids (Low-S diet), emphasizing plant-based foods and fat sources; and 2) a diet high in sulfur-containing amino acids (High-S diet), emphasizing animal protein and fat sources. A 14-day washout period will follow each intervention, in which participants will eat their typical diets. Intervention order will be randomly assigned through a computer-generated number sequence. At the conclusion of the second intervention, participants will be instructed to resume normal dietary habits and will be tracked for an additional 7 days to monitor study endpoints and related variables. Frequent communication between participants, the registered dietitian, and other study investigators will be sustained throughout the trial to ensure compliance with dietary and data collection and to reduce attrition.

Participants will be assessed prior to any dietary intervention to determine baseline demographics and characteristics, dietary habits, and measurements of endpoints of interest. High-S and Low-S meal plans will be designed by a registered dietitian trained in nutrient analysis, and detailed descriptions of each intervention will be discussed with participants. Participants meeting inclusion criteria will be consented at the screening clinic visit. Routine clinical examinations, assessments, laboratory evaluations, and sample collections will be completed at 5 clinic visits over a time period spanning approximately 35 days.

3.1 Study Participants and Recruitment

Highly motivated participants will be recruited from the Minneapolis-St. Paul metropolitan area. All participants will comply with the following predetermined inclusion and exclusion criteria:

3.1.1 Inclusion Criteria

Participants will be eligible to participate in the study if all of the following conditions exist:

1. Provide informed consent
2. Ambulatory and community dwelling
3. Able and willing to comply with the study schedule and procedures
4. 18 - 80 years of age

5. BMI between 18.5 – 40.0 kg/m²
6. Omnivorous or willing to consume animal products through duration of study

3.1.2 Exclusion Criteria

Subjects will be excluded from participation in the study if any of the following conditions exist:

1. Antibiotic use within 3 months
2. Planned antibiotic therapy within the period of the study, e.g., perioperative antibiotics.
3. Use of sulfonamides or sulfasalazine, as these sulfur-containing medications may confound results
4. Use of 5-aminosalicylates (5-ASA), as they are known to inhibit sulfidogenesis
5. History of anaphylactic food allergies, e.g., peanuts, seafood.
6. Food intolerances and allergies, including gluten sensitivity, lactose intolerance, and intolerance of high fiber dietary content.
7. Strict vegan eating practices, with refusal to consume animal products.
8. Planned use of oral probiotics while on study.
9. Serious, concomitant illness that, in the opinion of the Investigator, would interfere with evaluation of safety or efficacy, or put the participant at risk of harm from study participation.
10. Significant alcohol use, defined as > 20 g/day in females and > 30 g/day in males for a period of 3 months within one year prior to screening.
11. Underlying chronic gastrointestinal disease that can cause diarrhea, including short bowel syndrome, irritable bowel syndrome, malabsorption, and celiac disease.
12. History of partial or complete colectomy.
13. History of malabsorptive bariatric surgery.
14. Currently participating in another clinical study.
15. Legally incompetent and unable to understand the study's purpose, significance and consequences, and to make decisions accordingly.

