2.5 Study Outcome Measures

2.5.1 Primary Outcome Measures

Primary outcome measures of this study include:

1. Concentration of H₂S, CH₄, H₂, and methanethiol (CH₃SH) in fecal headspace samples measured by gas chromatography spectrometry (GC).
2. Changes in fecal bacterial composition (pre- vs. post-diet) associated with High-S vs. Low-S diets.

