4.2 Initial Screening Visit

The study will be explained to potential participants qualified from initial recruitment. Consent will be obtained at this time that will go over all the procedures and studies involved. During this visit the medical history will be collected and inclusion/exclusion criteria will be thoroughly reviewed. The following procedures will occur after the consent form is signed:

- Thorough review of the study, including involved procedures
- Medical history, including medications over the previous 12 months, and demographics
- Vital signs (heart rate, blood pressure, respiration rate)
- Height and weight measurement
- Review of methods used to record and measure food consumption during the study, to be conducted by dietitian.
- Three-day diet record is initiated following this visit, to be completed prior to visit 1 (baseline).
- Urine collection kit provided, to be completed prior to visit 1
- Link provided for web-based NCI Diet History Questionnaire III (DHQ III) to assess the baseline diet of subjects prior to entry into the study

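### The probiotic exclusion has no look-back, so the effect of stopping shortly before baseline can be mistaken for an effect of the first diet in the within-diet comparisons

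*Combined protocol and SAP*

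**What the plan says.** Section 3.1.2 treats antibiotics in both directions. Exclusion 1 looks back ("Antibiotic use within 3 months") and exclusion 2 looks forward ("Planned antibiotic therapy within the period of the study, e.g., perioperative antibiotics"). Probiotics have only the forward half: "Planned use of oral probiotics while on study". Nothing says when being on study begins.

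Criteria are reviewed at the screening visit (section 4.2), which also records "Medical history, including medications over the previous 12 months, and demographics". No eligibility rule for probiotics is tied to that history. The first diet starts straight after the Day 0 visit (section 4.3).

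One of the two primary outcome measures in section 2.5.1 is "Changes in fecal bacterial composition (pre- vs. post-diet) associated with High-S vs. Low-S diets". The Protocol Summary makes the Day 0 to Day 7 change in H2S the within-group comparison and the two diets' Day 7 values the between-group comparison. Section 6.1 tests both kinds of comparison with paired t-tests and states no period term.

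**The concern.** The antibiotic look-back shows that the authors wanted a baseline microbiota not recently disturbed by an outside agent. Exclusion 8 does not give that protection for probiotics: a daily user passes by agreeing to stop.

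If that person's flora is still readjusting at Day 0, the readjustment continues while the first diet is eaten. The within-diet comparison has no concurrent control, so for that person the two effects cannot be told apart. The study is meant to measure how large a dietary effect can be and to inform the size of a trial in patients with ulcerative colitis. A within-diet change that includes a stopping effect would be carried into that planning.

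**Working it through.** The plan states no power, SD or effect size (section 6.1), so there is no figure of its own to reproduce. The check is of eligibility, then timing, then size.

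**1. Eligibility.** Take someone who used the agent until shortly before screening and does not intend to use it again.

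| Agent | Past use | Planned use | This person |
|---|---|---|---|
| Antibiotics (exclusions 1, 2) | excluded within 3 months | excluded | excluded |
| Oral probiotics (exclusion 8) | not addressed | excluded | eligible |

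**2. Timing.** No minimum gap between screening and Day 0 is stated. The tasks between them are a three-day diet record and a urine collection (section 4.2), with small stool samples on Days -4 and -2, each ± 2 days (section 3.4.1). Stopping a few days before baseline is therefore permitted.

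**3. Expected bias.** Let p be the share of participants who stop shortly before baseline. Let s be the shift that stopping causes between Day 0 and Day 7, in SDs of the 7-day within-person change. Assume the effect is over by the second diet's baseline at Day 21.

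- Mean period-1 change: bias = p × s.
- Each diet's change pooled over both periods: about half the participants take that diet first, so bias = p × s / 2.
- High-S minus Low-S: p × s / 2 − p × s / 2 = 0 in expectation.

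| p (assumed) | s (assumed) | Period 1 | Each diet, pooled |
|---|---|---|---|
| 0.10 | 0.5 | 0.05 | 0.025 |
| 0.10 | 1.0 | 0.10 | 0.05 |
| 0.20 | 0.5 | 0.10 | 0.05 |
| 0.20 | 1.0 | 0.20 | 0.10 |

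If by chance every stopper took the same diet first, that diet's pooled bias would reach the period-1 figure.

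**4. Noise in the between-diet contrast.** With m stoppers among n participants and order set by a fair coin, the chance imbalance in the difference between the two 7-day changes has mean 0 and SD s × √m / n. For m = 3, n = 30, s = 0.5 this is 0.5 × 1.732 / 30 = 0.029. For m = 3, n = 15, s = 1.0 it is 1.732 / 15 = 0.115. These are the ends of the range over n = 15 (section 3) and n = 30 (Protocol Summary).

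**5. False-positive rate.** Paired t-tests at two-sided 5% were simulated with no diet effect, 20% stoppers and s = 0.5 or 1.0 (100,000 runs each).

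| n | Within-diet, s = 0.5 | Within-diet, s = 1.0 | Between diets (7-day changes) |
|---|---|---|---|
| 15 | 5.2% | 5.9% | 4.9-5.0% |
| 30 | 5.7% | 7.3% | 4.9-5.0% |

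**The case against.** **Stopping may come earlier than feared.** If being on study starts at consent, the product is stopped some days before Day 0. The documents do not say how long its organisms persist or link probiotics to H2S. This stands as a limit on size: the effect may be largely over by baseline. It does not close the gap, because nothing ensures an adequate interval.

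**The main contrast is protected.** The first primary objective compares the two diets, and the between-group H2S endpoint uses end-of-diet values, so the Day 0 sample does not enter it. This stands. A reader might infer that the High-S versus Low-S result is biased; with random order it is not, in expectation.

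**The data already allow a check.** Medication history, medication review at each visit, the daily log and repeated pre-diet stools could support a sensitivity analysis. This stands in part: none of these explicitly captures probiotics, and with 15 to 30 participants the stoppers would be few.

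**A stronger reading of exclusions 3 and 4.** These say "Use of sulfonamides or sulfasalazine, as these sulfur-containing medications may confound results" and "Use of 5-aminosalicylates (5-ASA), as they are known to inhibit sulfidogenesis", with no window. A reader might infer that a regular user of these drugs who stops at Day 0 is also eligible. The text does not support that: criteria are reviewed at screening, and someone using the drug then is excluded on the plain words. Recent 5-ASA users should also be rare, since the volunteers are healthy and exclusion 11 removes "Underlying chronic gastrointestinal disease that can cause diarrhea, including short bowel syndrome, irritable bowel syndrome, malabsorption, and celiac disease". Inflammatory bowel disease is not among those examples, but section 1 describes ulcerative colitis as a cause of diarrhea. What remains is an undefined window for someone who stopped just before screening. That calls for a minor clarification and is not a separate defect.

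**Conclusion.** The point holds for probiotics, as a small and cheaply remedied weakness. Exclusion 8 admits a recent regular user, and any stopping effect still under way at Day 0 is inseparable from the first diet in the uncontrolled within-diet comparison. On the assumed range the expected bias is 0.05-0.20 SD in period 1 and about 0.03-0.10 SD in each diet's pooled change, in a direction the documents do not let one predict. The between-diet contrast is unbiased in expectation, with added chance imbalance of about 0.03-0.12 SD.

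These sizes rest wholly on assumed values of p and s, on an effect that runs through the first week and is over by Day 21, and, for H2S, on probiotics affecting it at all. If few participants use probiotics, or the effect fades before Day 0, the bias is close to nil.

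**What to change.** Reword exclusion 8 to cover two things: oral probiotics taken within a stated window before the first baseline stool sample, and probiotics planned during the study. Fourteen days could serve as an example because the protocol already uses it as the diet washout. The documents do not establish that it suits probiotics, so the sponsor should confirm the length.

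Apply the rule from the screening medication history, asking about probiotics by name, and re-check it at the Visit 1 medication review. Recent users can defer Day 0 instead of being refused. For anyone already enrolled, report the within-diet changes with and without recent users, as far as the records identify them.

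In the same amendment, state the window that exclusions 3 and 4 are meant to carry, taking care not to make them narrower than intended.

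The cost is a wording change, a short delay for recent probiotic users, and perhaps a few more screen failures.

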3.2 Diet Intervention Design

Two intervention diets will be designed by a registered dietitian trained in nutrient analysis. A registered dietitian will provide detailed instructions for each intervention diet, and educational materials will be developed to indicate foods with high and low contents of SAAs as well as example meal plans for participants to reference. Dietary instructions will be based on the following table:

Table 1. Guidelines for intervention diets

High-S Diet (Emphasize animal-based foods)	Low-S Diet (Emphasize plant-based foods)
Meats: beef, pork, lamb, veal, venison, goat, processed meats (ham, bacon, bologna, salami, sausages, hot dogs, deli or lunch meats), poultry, seafood, shellfish	Cooked lentils and beans, excluding soy beans or soy bean-derived products
Dairy Products: cheese, milk, yogurt, ice cream, sour cream	Dairy alternatives: almond milk, rice milk, hemp milk, coconut milk, cream substitutes
Eggs	Egg substitutes
Animal-derived fats: butter, lard	Plant-derived fats: oils (e.g., vegetable, olive, safflower, cottonseed, cod liver, coconut, peanut, sesame)
Grains: white breads, pastas, rice	Grains: whole wheat, brown rice, bulgur, buckwheat, barley, oats, fiber-containing breakfast cereals
Limited intake of vegetables	Fresh/frozen vegetables
Limited intake of fruit	All fruit
Beverages: fruit juices, mineral water, sulfited wines, coffee, tea	Beverages: fruit and vegetable juices, coffee, tea, distilled spirits, beer
Soy Products: soy milk, tofu, tempeh, miso, soy crisps, dried soy beans	Snack foods: granola bars, popcorn, pretzels, potato chips, rice cakes
	Nuts and seeds
Condiments: mayonnaise, dairy-based salad dressings	Condiments: oil-based salad dressings; ketchup, mustard, canned sauces and gravies

During the Low-S diet intervention, participants will be advised to completely avoid foods high in SAAs, strictly eating foods included on the “Low-Sulfur Foods” list. During the High-S intervention, participants will be instructed to eat foods strictly from the “High-Sulfur Foods” list. Participants will record time and location of food intake and any deviations from the prescribed diet in the provided study log. Participants will have access to a registered dietitian throughout their participation in the study to assist with any issues regarding the trial or the diet.

3.3 Dietary Intake Assessment

Dietary intake data will be collected before, during, and after the intervention period to estimate usual total energy intake and macro- and micronutrient composition. Two methods of dietary assessment will be used: food frequency questionnaires (FFQs) and 3-day diet records. The National Cancer Institute’s Diet History Questionnaire III (DHQ III) is a freely available web-based FFQ. A web-based version of the DHQ III will be completed by participants at their baseline clinic visit (Day 0), in which they will be asked about their usual dietary intake over the past year.

Participants will be instructed to record their daily intake of foods and beverages during each 7-day intervention period. Throughout the intervention, participants will be instructed to maintain normal physical activity, sleep habits, and caffeine consumption (coffee and tea). A registered dietitian will be in contact with participants throughout the interventions to monitor compliance with the High-S and Low-S diets. Three-day diet records will be completed by participants prior to the intervention start date, once during each intervention, and twice during the washout period,

and one week after the conclusion of the second intervention diet to determine independent, ad libitum dietary habits. A registered dietitian trained and certified in the University of Minnesota's Nutrient Data System for Research (NDSR) dietary interviewing and assessment protocols will instruct participants on methods for accurate quantification and recording of dietary intake. DHQ III data will be analyzed with Diet*Calc software developed by the National Cancer Institute. Analysis of 3-day diet records will be performed using NDSR data output.

3.3.1 Tolerability and Feasibility

There are many difficulties associated with examining the effects of dietary components on health, and subject compliance is of major importance to the outcome of any dietary trial. It is extremely difficult to control for subject compliance completely; however, daily diet records during each intervention and 3-day diet records in each standard diet phase, coupled with frequent contact by study staff, will improve participant adherence.

Participants will be provided with a study log at the baseline clinic visit (Day 0). Data recorded in the study log will be reviewed by study investigators at each contact with participants and will be recorded for data analysis. Participants will be instructed to record the following during each day of the study period:

- Adverse events, with specific attention paid to gastrointestinal symptoms including bloating, gas, abdominal pain, constipation, and loose stools
- New medications and/or any medication use – dose and frequency of administration
- Time of bowel movements and stool consistency
- Physical activity

Since the intention of this project is to generate pilot data for a longer randomized trial, approximating compliance for a prolonged period of time (≥ 3 months) is necessary for the design of future interventions. A questionnaire will be developed to assess participants' input on tolerability and feasibility for each dietary intervention.

3.4 Sample Collection

3.4.1 Fecal Samples

Fecal samples will be collected to assess gut microbial composition (via 16S sequencing) and to evaluate concentrations of fecal gases related to sulfur metabolism (via GC). Participants will collect samples in disposable commode specimen containers placed under the toilet seat prior to a bowel movement. Samples collected from the center of the specimen will be used for DNA sequence analysis. Larger collection tubes will be provided for intact stool samples for fecal headspace analysis and dry weight determination. The remainder of fecal specimens collected on-site will be transferred into sterile containers. Specimens will be put in the freezer until transfer to the investigator's lab. Full samples will be collected at designated study visits. Participants will also be asked to collect intermittent samples in collection tubes throughout the study. These will be collected on days (± 2 days) -4, -2, 3, 5, 9, 11, 16, 18, 23, 25, 30, and 32. These samples will be stored in the participant's freezer and collected at each study visit. Participants will also record all bowel movements in their study log.

3.4.2 Urine Samples

24-hour urine collections will take place per PI discretion at baseline (Day 0; Day 0±2 days), at the end of the first diet intervention (Day 7; Day 5±2 days), at the end of the washout period (Day 21; Day 19±2 days), and at the end of the second diet intervention (Day 28; Day 26±2 days). Participants will collect all urine for a 24-hour period in a collection bottle(s), which will be stored in the refrigerator. Participants will be asked to note the exact time they begin and complete their urine collection. The entire 24 hour sample (all urine containers) will be returned after completion of the 24-hour period. Samples collected will be used for urine sulfate analysis.

3.4.3 Blood Samples

Blood (10 mL) will be collected per PI discretion in the clinic at visits 1, 2, 3, 4, 5, and 6 in Vacutainer Blood Collection Tubes. Blood for clinical laboratory assessment will be collected into tubes containing lithium heparin as anticoagulant. The tubes will be inverted carefully 3-5 times to mix blood and anticoagulant, and kept at room temperature until centrifugation, which will be done within 15 minutes of collection. Blood for measurement of TMAO and metabolites will be collected into a gel-barrier tube and allowed to clot for 30 minutes. Centrifugation of all samples will be carried out for 15 minutes at 1400 RCF (relative centrifugal force) at refrigerated temperature. The top layer (serum or plasma) will be collected and frozen at -80°C.

3.5 Gas Concentration Measurement

Gases produced by fecal samples will be analyzed by GC. Approximately 10g of fecal material will be transferred to a gas-tight septum jar and incubated at 37°C for 2 hours. After incubation, 5mL gas samples will be removed with a syringe and injected into 10ml headspace vials, pre-purged with nitrogen gas. H₂S and CH₃SH concentration will be measured using a gas chromatograph outfitted with a sulfur chemiluminescence detector (GC-SCD). CH₄ concentration will be measured using a gas chromatograph with a flame ionization detector (GC-FID) and CO₂/H₂ is quantified using a gas chromatograph equipped with a thermo-conductivity detector (GC-TCD). Calibration gases will be used as standards for all quantifications. All measurements will be normalized to mL per gram (dry weight) fecal material. Dry weight is calculated by taking a known mass of wet fecal material, baking it at 95°C under vacuum for ≥ 16 hours, weighing the dried fecal material and calculating the ratio of dry weight / wet weight.

3.6 16S Sequencing

Fecal bacteria composition will be characterized using high throughput 16S rRNA gene sequence analysis.

3.6.1 DNA Extraction from Fecal Samples

DNA will be extracted from ~0.25g aliquots of fecal samples using a PowerSoil DNA Extraction Kit (Mo Bio Laboratories, Carlsbad, CA) performed according the manufacturer's instructions. Approximately 100 ng of DNA will be used for PCR amplification of the 16S rRNA gene in samples.

3.6.2 Amplification of 16S rRNA Gene and Sequencing

The V5+V6 hypervariable regions of the 16s rRNA gene will be amplified using primers specific for that region. Amplicons obtained from individual samples will be pooled in equimolar ratios

prior to sequencing. Paired end sequencing will be performed using the Illumina MiSeq (Illumina Inc, San Diego, CA) platform at the University of Minnesota Genomics Center (UMGC). Sequence data will be analyzed using the MOTHUR program³⁰ for taxonomic assignment and alpha/beta diversity. Sequence datasets will be compared by principle component analysis.

